4.6 Treatment Assignment and Blinding

4.6.1 Methods for Assigning Treatment Groups

An IXRS will be used for randomization to a treatment group and assignment of blinded investigational product kit numbers.

A subject is considered randomized into the study when the investigator or designee notifies the IXRS that the subject meets eligibility criteria and the IXRS provides the assignment of blinded investigational product kit numbers to the subject.

Prior to randomization, subjects will be stratified by study site (non-Japanese and Japanese), then subjects will be stratified by blood eosinophil count (\geq or < 250 cells/ μ L) and by ICS dose level (medium or high). Subjects taking maintenance OCS will be automatically assigned to the high-dose ICS strata. There will be a total of 8 strata; 4 strata for non-Japanese subjects and 4 identical strata for Japanese subjects (see Section 3.1.1 for strata descriptions).

Subjects will then be randomized at a 1:1:1:1 ratio to receive either MEDI9929 (280 mg [Q2W], 210 mg [Q4W], or 70 mg [Q4W]) or placebo.

Investigational product (MEDI9929 or placebo) must be administered the same day the investigational product is assigned. If there is a delay in the administration of investigational product such that it will not be administered within the specified timeframe, the study monitor must be notified *immediately*.

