4.8 Statistical Evaluation

4.8.1 General Considerations

Data will be provided in data listings sorted by treatment group and subject number. Tabular summaries will be presented by treatment group. Categorical data will be summarized by the

number and percentage of subjects in each category. Continuous variables will be summarized by descriptive statistics, including mean, standard deviation, median, minimum, and maximum. Confidence intervals (CIs) will be two-sided and all efficacy analyses will be conducted with a two-sided test at the 0.1 significance level, unless otherwise stated. Baseline value will be defined as the last valid assessment prior to the first administration of investigational product on Day 1.

No missing data will be imputed for the primary endpoint. Missing data imputation methods for the secondary endpoints will be specified in the statistical analysis plan (SAP). The primary endpoint will be tested using a stepdown method for 3 hypotheses (from the high dose [280 mg Q2W] to the medium dose [210 mg Q4W] to the low dose [70 mg Q4W] when compared with placebo) to maintain the overall type-1 error rate at 0.1 (two sided). Nominal p-values will be provided for the selected secondary efficacy endpoints (pulmonary function, ACQ-6, AQLQ(S)+12, and Asthma Daily Diary) without multiplicity adjustment.

For the selected secondary efficacy endpoints that are continuous variables, a generalized linear mixed model using a linear contrast test including treatment group, visit, treatment-by-visit interaction, baseline blood eosinophil count (≥ or < 250 cells/µL), baseline ICS dose level (medium or high), and the respective baseline measure for the given endpoint as fixed effects may be used to compare the change from baseline at Week 52 for each efficacy endpoint between the individual MEDI9929 dose groups and the placebo group, respectively. No p-values will be reported for other PROs. Additional details of statistical analyses will be described in the SAP.

The intent-to-treat (ITT) population is defined as all subjects who are randomized and receive any investigational product. Treatment group will be assigned according to the initial randomization, regardless of whether subjects receive an investigational product different from that to which they were randomized. This is the primary efficacy population.

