4.8.3.2 Secondary Efficacy Analyses

Efficacy Outcomes in Pre-specified Subpopulations of Asthma

The primary endpoint of a reduction in the annualized AER measured at Week 52 and two other secondary endpoints of change from baseline in FEV_1 and in overall symptom score at Week 52 will be analyzed by the following pre-specified subpopulations of asthma:

1) eosinophilic and non-eosinophilic; 2) Th2 high/low (Corren et al, 2011); 3) FE_{NO} high/low; 4) periostin high/low; 5) current post-BD FEV₁ reversibility; and 6) allergic and non-allergic asthma.

Pulmonary Function

The effect of MEDI9929 on pulmonary function as measured by pre- and post-BD FEV_1 and FVC at the site, and PEFR at home will be assessed during the study. Change from baseline in the mean values and percent change from baseline at various time points will be summarized using descriptive statistics. Change from baseline in the mean values and percent change from baseline of FEV_1 and FVC at Week 52 will be analyzed.

Additional Analyses of Asthma Exacerbation

The analysis of exacerbations will also be conducted specifically for severe asthma exacerbations (hospitalizations). In addition, asthma exacerbations and severe asthma exacerbations through Week 64 will also be summarized.

Time to first asthma exacerbation and time to first severe asthma exacerbation will be analyzed as a supportive efficacy analysis for the primary objective using a log-rank test. Incidence of asthma exacerbations will also be evaluated by the proportion of subjects having one or more asthma exacerbations and one or more severe asthma exacerbations during the study.

Optimal Dose and Regimen

Dose response may be evaluated based on quadratic and linear negative binomial regression models to detect the dose response. The E_{max} model may be generated to determine the minimum effective dose. The details of the dose response analysis will be described in the SAP.

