4.8.4 Patient-reported Outcomes

Asthma Control Questionnaire-6

Asthma control will be evaluated by ACQ-6. The change from baseline in the mean ACQ-6 score will be analyzed. The proportion of subjects with change from baseline in the mean ACQ-6 score ≥ 0.5 during the study and the proportion of subjects who are well controlled (mean ACQ-6 score of ≤ 0.75), partially controlled (0.75 < mean ACQ-6 score ≤ 1.5), and uncontrolled (mean ACQ-6 score ≥ 1.5) will be compared between the individual MEDI9929 group and placebo group using the Fisher's exact test. A stratified log-rank test will be conducted to compare the time to first asthma control defined as a reduction from baseline in the mean ACQ-6 score ≥ 0.5 is first observed and the time to first partially control (0.75 < mean ACQ-6 score ≤ 1.5) and well controlled (mean ACQ-6 score of ≤ 0.75).

Asthma Daily Diary

Each item of the Asthma Daily Diary will be summarized showing change over time compared to baseline scores. Baseline will be defined as the 14-day period prior to dosing on Day 1 (ie, Day -15 to Day -1). Asthma Daily Diary data will be summarized as biweekly (14 day) means post dosing on Day 1. The change from baseline in the following endpoints will be analyzed:

- The mean symptom scores for daytime severity, daytime frequency, nighttime severity, and overall symptom score, where overall symptom score is the average of scores of daytime severity, daytime frequency, and nighttime severity
- The mean scores for the activity limitation questions
- Number of times rescue medication is used: daytime use, nighttime use, total rescue medication use (daytime + nighttime)
- The proportion of nights without nocturnal awakening and the proportion of nights without asthma-related nocturnal awakening (no awakening or wakening without rescue medication use)

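### ACQ-6 proportions are compared with an unstratified Fisher's exact test: valid, but conservative and out of line with the stratified design

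*Protocol*

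**What the plan says.** - **ACQ-6 proportions (Section 4.8.4).** The proportion with a change of at least 0.5, and the proportions well, partially and uncontrolled, are compared between each MEDI9929 dose and placebo "using the Fisher's exact test". No strata or covariates are named.
- **ACQ-6 time to event (same paragraph).** "A stratified log-rank test will be conducted to compare the time to first asthma control", and likewise the times to partial and good control. The stratification factors are not listed.
- **Exacerbation time to event (Section 4.8.3.2).** Times to first exacerbation and first severe exacerbation are analysed "using a log-rank test". The text does not say whether it is stratified.
- **Randomisation (Section 4.6.1).** "There will be a total of 8 strata; 4 strata for non-Japanese subjects and 4 identical strata for Japanese subjects", formed by region, eosinophil count (cut at 250 cells/μL) and ICS level. Then: "Subjects will then be randomized at a 1:1:1:1 ratio".
- **Other models.** The primary negative binomial model (Section 4.8.3.1) includes eosinophil and ICS category and leaves out region. The mixed model that may be used for continuous secondary endpoints (Section 4.8.1) includes the same two factors and the baseline value.
- **Error level (Section 4.8.1).** "all efficacy analyses will be conducted with a two-sided test at the 0.1 significance level" unless stated otherwise. For ACQ-6 among others, "Nominal p-values will be provided for the selected secondary efficacy endpoints", without multiplicity adjustment.

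**The concern.** The plan adjusts for eosinophil and ICS category in its primary model and foresees the same for its continuous secondary endpoints. It also stratifies the time-to-event analysis of the very ACQ-6 thresholds at issue. The proportions based on those thresholds get a test that can use neither the strata nor the baseline score, and the protocol gives no reason.

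Two things follow. First, Fisher's exact test rejects less often than its nominal level when the two arms are independent binomial samples, so some power is given away. Second, analyses of one questionnaire rest on different adjustment sets, so a difference between the responder result and the time-to-control result could be partly an artefact of method. Baseline score plausibly matters: entry requires an ACQ-6 of at least 1.5 twice during screening, and reaching 0.75 or less may well depend on how far above 1.5 a subject starts.

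**Working it through.** **Inputs from the protocol.** 138 per arm (Table 3.1.2-1), or 124 before the dropout allowance (Section 4.8.2); two-sided 10% level (Section 4.8.1); 1:1 for each dose against placebo.

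**Assumed inputs.** The protocol gives no ACQ-6 response rate, target difference or prognostic strength of the strata. Ranges are used for all three.

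**Step 1: reproduce the plan's own figure.** No power is stated for the ACQ-6 proportions. The only related figure is the primary sample size. With placebo rate 0.7, treated rate 0.7 × 0.6 = 0.42, dispersion 0.7 and one year of follow-up:

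n = (1.645 + 0.842)² × (1/0.7 + 1/0.42 + 2 × 0.7) / (ln 0.6)² = 6.18 × 5.21 / 0.261 = 123.4, rounded up to 124. Then 124/0.9 = 137.8, rounded up to 138. Both match.

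**Step 2: true size and power by exact enumeration.** For response rates p (placebo) and q (active), rejection probability = Σₓ Σᵧ Bin(x; n, p) × Bin(y; n, q) × 1{p-value(x, y) ≤ 0.10}. Size sets q = p. For power, q is chosen so that the Pearson chi-square test has 80% power.

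| Placebo rate (n = 138) | Size, Fisher | Size, chi-square | Difference for 80% chi-square power | Fisher's power there |
|---|---|---|---|---|
| 10% | 6.5% | 10.4% | 10.7 points | 75.4% |
| 20% | 7.4% | 10.0% | 13.1 points | 75.7% |
| 30% | 7.6% | 10.2% | 14.5 points | 76.2% |
| 40% | 7.5% | 9.8% | 14.8 points | 76.4% |
| 50% | 8.1% | 10.4% | 14.7 points | 76.4% |
| 60% | 7.5% | 9.8% | 13.9 points | 76.0% |
| 70% | 7.6% | 10.2% | 12.6 points | 75.7% |

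The loss is 3.6 to 4.6 points at 138 per arm, and 3.8 to 5.0 at 124. Chi-square uses no strata either, so this part is due to discreteness alone.

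**Step 3: the loss depends on where power lies.** At 138 per arm and a placebo rate of 40% (chi-square v Fisher): a 10-point difference gives 51.6% v 46.7%; 18 points gives 91.7% v 89.7%; 25 points gives 99.5% v 99.3%. At a placebo rate of 5% the loss at 80% chi-square power is about 8 points (Fisher 72.3%).

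**Step 4: what the strata add.** Simulation with 40,000 trials per setting, four equal strata balanced across arms, 138 per arm, overall placebo rate 50%. The strata differ in log-odds with the SD shown. CMH = Cochran-Mantel-Haenszel.

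| Stratum SD (logit) | Odds ratio | CMH | Chi-square | Fisher | CMH − Fisher | CMH − chi-square |
|---|---|---|---|---|---|---|
| 0 | 1.9 | 83.2% | 83.2% | 80.1% | 3.1 | 0.0 |
| 0.25 | 1.9 | 82.7% | 82.6% | 79.2% | 3.5 | 0.0 |
| 0.5 | 2.0 | 86.2% | 85.4% | 82.3% | 3.9 | 0.8 |
| 0.75 | 2.0 | 84.8% | 81.8% | 78.2% | 6.6 | 2.9 |
| 1.0 | 2.1 | 85.7% | 81.4% | 77.6% | 8.1 | 4.3 |

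Differences are in points, from unrounded values. At SD 1.0 and odds ratio 2.0, where power is somewhat lower, the gap reaches about 10 points: 74.3% v 64.2% at a placebo rate of 20%, and 79.3% v 69.5% at 60%. The last column is the part due to ignoring the strata: about 0 if they are weak, about 1 if moderate, and 3 to 5 if strong.

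**The case against.** The case against acting is that nothing is broken. Fisher's test is valid under this randomisation, holds type I error below 10% and biases nothing. A proportion and a time to event may properly be tested by different methods. The secondary endpoint listed in Section 2.2.2 is change from baseline in ACQ-6, for which an adjusted model is foreseen. The proportions are supportive, unpowered, and outside the step-down procedure. All of this stands, and it sets the weight of the point.

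Several stronger readings are tempting, and the documents do not support them:

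- *A fixed loss of 4 to 5 points.* This needs response rates that the protocol does not give. Steps 3 and 4 show a range from near 0 to about 10.
- *The ignored strata cause the loss.* With weak or moderate strata nearly all of it is discreteness, and an unstratified chi-square test would recover most of it. The protocol says nothing on how prognostic the strata are for ACQ-6 response.
- *Confidence intervals are too wide.* Section 4.8.4 specifies no interval for these proportions.
- *The exacerbation log-rank tests are unstratified.* Section 4.8.3.2 is silent on this, and Section 4.8.1 leaves further detail to the SAP, which is not at hand. It is a matter for clarification, not a shown defect.

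One further objection is fair: four strata are not the eight used to randomise, and Section 3.1.1 lets ICS stratification lapse for late Japanese enrolment. But the primary model already omits region, and ICS level remains a baseline variable. Four strata therefore match the adjustment set the protocol uses elsewhere.

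**Conclusion.** The point holds as one of efficiency and consistency. The protocol itself fixes an unstratified exact test for the ACQ-6 proportions, in a stratified trial and beside a stratified test of the same thresholds.

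- **Size of the test:** about 6.5% to 8.1% at a nominal 10%, for 138 per arm and common response rates of 10% to 70%. This follows by enumeration and needs no assumption about the strata.
- **Power:** roughly 4 points lost near 80% power, mostly from discreteness. The loss is close to 0 at very high power and up to about 8 to 10 points if the strata are strongly prognostic. These figures rest on assumed response rates and stratum effects.
- **Reach:** supportive proportions with nominal p-values. The primary test, the step-down procedure and the listed endpoint of mean ACQ-6 change are unaffected.

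The calculations treat each proportion as a separate binary outcome. Section 4.8.4 does not say whether the three control categories are tested jointly or one at a time.

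**What to change.** In Section 4.8.4, compare each dose with placebo by a Cochran-Mantel-Haenszel test stratified by eosinophil count and ICS level, or by a logistic model with those two factors and baseline ACQ-6. Choose one in advance, and report the adjusted difference or odds ratio with its 90% confidence interval. State whether the control categories are tested jointly or singly. Use baseline ICS level for subjects enrolled after ICS stratification is lifted.

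Name the factors of the stratified log-rank test in Section 4.8.4. For consistency, state in Section 4.8.3.2 that the exacerbation log-rank tests are stratified by the same factors.

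This is a free improvement: it takes a few lines of text and uses only baseline data already collected, with no added subjects, visits or assessments. If the SAP already makes these changes, the protocol need only be aligned with it.

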- 8. Subjects must have a morning pre-BD FEV₁ value of \geq 40% and \leq 80%, predicted at 2 Screening Visits. The first time must be at either Visit 1 (Week -5) or Visit 2 (Week -4), and the second time must be at Visit 3 (Week -1).
- 9. Subjects must have an ACQ-6 score of ≥ 1.5 twice during screening. The first time must be at Visit 1 (Week -5). The second time may be at either Week -2 (taken from home recording on the electronic patient-reported outcome [ePRO] device) or at Visit 3 (Week -1).
- 10. At Visit 4 (Week 0, Day 1), subjects must have at least one of the following over the previous 7 days from the ePRO device:
 - > 2 days with a daytime or nighttime symptoms score \ge 1 (Asthma Daily Diary); or
 - \circ ≥ 1 awakening due to asthma requiring rescue medication use; or
 - Rescue/reliever short-acting β2 agonist (SABA) use > 2 days.
- 11. Subjects must have a documented history of at least 2 asthma exacerbation events OR at least 1 severe asthma exacerbation resulting in hospitalization (admission to the hospital for at least 24 hours) within the 12 months prior to Visit 1 (Week -5). To qualify as an asthma exacerbation event, administration of a burst of systemic corticosteroids for at

least 3 consecutive days must have been required for the treatment of the asthma exacerbation, or the asthma exacerbation resulted in an emergency department (ED) visit which required systemic corticosteroids for at least 3 consecutive days or hospitalization. For subjects receiving maintenance OCS, a temporary doubling of the stable existing maintenance dose for at least 3 days qualifies.

- 12. If on allergen-specific immunotherapy subjects must be on a maintenance dose and schedule for at least 2 months prior to Visit 1 (Week -5).
- 13. Subjects must meet the all of following criteria at Visit 4 (Week 0, Day 1) prior to randomization:
 - Subjects must demonstrate acceptable inhaler, peak flow meter, and spirometry techniques during screening/run-in period (from Visit 2 to Visit 4).
 - Subjects must demonstrate ≥ 70% compliance with usual asthma controller ICS/LABA during the screening/run-in period (from Visit 2 to Visit 4) based on the Asthma Daily Diary.
 - Subjects must demonstrate ≥ 80% compliance with required use of the ePRO device; 80% compliance is defined as completing the Asthma Daily Diary for any 8 mornings and any 8 evenings in the previous 10 days of the screening/run-in period.

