4.3.2.2 Asthma Control Questionnaire-6

The ACQ is a patient-reported questionnaire assessing asthma symptoms (ie, night-time waking, symptoms on waking, activity limitation, shortness of breath, wheezing) and daily rescue bronchodilator use and FEV₁ (Juniper et al, Oct 1999). The ACQ-6 is a shortened version of the ACQ that omits the FEV₁ measurement from the original ACQ score. Questions are weighted equally and scored from 0 (totally controlled) to 6 (severely uncontrolled). The mean ACQ score is the mean of the responses. Mean scores of \leq 0.75 indicate well-controlled asthma, scores between 0.75 and \leq 1.5 indicate partly-controlled asthma, and a score > 1.5 indicates uncontrolled asthma (Juniper et al, 2006). Individual changes of at least 0.5 are considered to be clinically meaningful (Juniper et al, 2005).

The study center staff will provide initial training on the ePRO device at Visit 1 (Week -5) in order for the subject to complete the screening ACQ-6 at the study center. The ePRO device will remain at the study center until Visit 2 (Week -4).

At Visit 2 (Week -4), study center staff will provide training as described in Section 4.3.2 and will give the subject the ePRO device to take home. The subject will complete the ACQ-6 weekly during the Screening/Run-in period. The Visit 2 (Week -4), Visit 3 (Week -1), and Visit 4 (Week 0, Day 1) ACQ-6 will be completed at the study site on the ePRO device. Subjects will be prompted to complete the ACQ-6 at Week -3 and Week -2 at home on the ePRO device. Once randomized, subjects will be prompted to complete the ACQ-6 every 2 weeks at home on the ePRO device through Week 64.

Subjects must have an ACQ-6 score of ≥ 1.5 twice during screening. The first time must be at Visit 1 (Week -5). If the ACQ-6 score is not ≥ 1.5 at Visit 1 (Week -5), then the subject should not continue in the study (screen failure). The second time the subject must have an ACQ-6 score of ≥ 1.5 may be at either Week -2 (at home on the electronic patient-reported outcome [ePRO] device) or at Visit 3 (Week -1).

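### ACQ-6 time-to-first-control analysis: a 0.5-point drop is called control even when the score is still in the uncontrolled band, and partial control can be counted with no improvement

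*Protocol*

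**What the plan says.** Protocol Section 4.8.4 sets out three time-to-first events for the ACQ-6, compared by a stratified log-rank test:

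- "time to first asthma control defined as a reduction from baseline in the mean ACQ-6 score ≥ 0.5 is first observed";
- "the time to first partially control (0.75 < mean ACQ-6 score ≤ 1.5");
- "well controlled (mean ACQ-6 score of ≤ 0.75").

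The first two stand in one sentence, joined as "is first observed and the time to first partially control (0.75 < mean ACQ-6 score ≤ 1.5"), with no confirming score and no condition on baseline between them.

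The same section compares by Fisher's exact test the proportion with a 0.5-point change over the study, and the proportions in three control bands.

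Other sections bear on these definitions:

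- **Bands.** Section 4.3.2.2 states that "a score > 1.5 indicates uncontrolled asthma" and describes an individual change of 0.5 as clinically meaningful. It does not call such a change control.
- **Entry.** Section 4.1.2, criterion 9: "Subjects must have an ACQ-6 score of ≥ 1.5 twice during screening". The first score is at Visit 1; the second may be at Week -2 or at Visit 3. No ACQ-6 minimum applies on Day 1.
- **Baseline.** Section 4.8.1 takes the last valid value before the first dose, normally the Day 1 score.
- **Schedule.** Section 4.3.2.2: "Once randomized, subjects will be prompted to complete the ACQ-6 every 2 weeks at home on the ePRO device through Week 64".

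**The concern.** Two of the three event definitions do not measure what their names say. A change of 0.5 is a response threshold, yet Section 4.8.4 reports it as attainment of control. The partial-control event is a score threshold with no condition on where the subject started, in a trial whose entry threshold is the same number.

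At stake is how the results will be read. A statement that a given percentage of an arm reached asthma control, or reached it in a given median time, will be taken at face value. Under the present wording it would include subjects whom the protocol itself classes as uncontrolled at that moment. The partial-control figure would include subjects who were in or below that band before the first dose.

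**Working it through.** **1. Control label against the protocol's own bands (no assumptions).** Let the baseline score be b. The first event needs a score of b - 0.5 or lower; the uncontrolled band is any score above 1.5. A subject can meet both at once whenever b - 0.5 > 1.5, that is, b > 2.0. Example: b = 3.0 and a later score of 2.5 gives a reduction of 0.5, so the event is counted, and 2.5 > 1.5, so the subject is uncontrolled.

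**2. Partial control without improvement (no assumptions).** The ACQ-6 is the mean of six items, so scores move in sixths and 9/6 = 1.5 is attainable.

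- A subject who enters at 1.5 and never changes satisfies 0.75 < 1.5 ≤ 1.5 at the first post-dose score.
- A subject who qualified at Visit 1 and Week -2 but scored 7/6 = 1.17 on Day 1 and 1.5 later has worsened by 0.33 and is still counted.
- Section 4.8.4 states no restriction to subjects above 1.5 at baseline. It also places exactly 1.5 in both the partial and the uncontrolled band, whereas Section 4.3.2.2 counts only scores above 1.5 as uncontrolled.

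**3. How many subjects this could involve (assumptions needed).** The protocol gives no ACQ-6 mean, SD or reliability, so there is no figure to reproduce. I simulated scores with no true change:

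- true score normal, mean 2.0, 2.5 or 2.8, between-subject SD 0.7;
- observed score = true score + error, rounded to sixths, within-subject SD 0.1 to 0.6, visit-to-visit correlation 0 or 0.6;
- the protocol's entry rule, baseline on Day 1, then 52/2 = 26 two-weekly scores to Week 52.

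| Quantity | Within-subject SD | Share of subjects |
|---|---|---|
| Day 1 score already ≤ 1.5 | 0.2 to 0.6 | 2% to 20% |
| Any reduction ≥ 0.5 by Week 52, single score | 0.1 | about 4% |
| Same | 0.2 | 40% to 46% |
| Same | 0.3 | 64% to 70% |
| Same | 0.2 to 0.6 | 40% to 88% |
| Same, met at two consecutive scores | 0.2 to 0.6 | 15% to 71% |
| Any score ≤ 0.75, single score | 0.3 | 0% to 2.4% |

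A second set of assumptions (mean 2.3 or 2.7 before selection, between-subject SD 0.8, within-subject SD 0.3 to 0.6, correlation 0 or 0.7) gave 61% to 88% for any reduction ≥ 0.5 and 17% to 33% for a reduction ≥ 0.5 at Week 52 alone. At the first such reduction, 61% to 86% of those subjects still scored above 1.5.

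**4. Effect on the test.** With 138 per arm, two-sided 0.1 and an unstratified log-rank test, within-subject SD 0.3 or 0.5 and mean 2.0 or 2.5:

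- no true effect: rejection in 8% to 12% of runs, for single-score and for confirmed events alike (nominal 10%);
- an assumed true shift of 0.3: rejection in 95% to 100% for single scores and 90% to 100% for confirmed events.

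**The case against.** The strongest reply is that the analysis is peripheral and the comparison is sound. The ACQ-6 secondary endpoint in Section 2.2.2 is change from baseline at Week 52. Time to first control appears in neither the secondary nor the exploratory endpoint list, and secondary p-values are nominal. Measurement noise acts on all arms alike, and the placebo arm puts the raw proportions in context. Confirmation rules and risk sets are often settled in the SAP, and a first event makes no claim of lasting control. All of this stands, and it limits the point to interpretation. It does not rescue the label or the open risk set: the 0.5-point definition is fixed in the protocol text, and the conflict with Section 4.3.2.2 needs no simulation to see.

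A reader might go further and infer that a large share of subjects will reach control by noise alone because the partial-control and entry cut-offs coincide at 1.5. The documents do not support that. The share ever scoring ≤ 1.5 with no true change ranges from about 5% to 78% over the assumed means and SDs, and noise matters mainly just above the line: at SD 0.3 a true score of 2.0 crosses with probability 89%, 2.5 with 3%, and 3.0 with about 0%. The large shares belong to the 0.5-point event, which does not use 1.5; they come from 26 looks against one baseline score.

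Nor should one read every ACQ-6 proportion as an ever-during-study figure. In Section 4.8.4 that period is attached only to the 0.5-point proportion, not to the three bands.

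**Conclusion.** The point holds as a defect of definition and labelling, minor in consequence and cheap to correct. Two parts rest on the text alone: any subject with a baseline above 2.0 can be counted as having reached control while uncontrolled by Section 4.3.2.2, and a subject at or below 1.5 on Day 1 can be counted as reaching partial control without improving.

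The sizes are conditional. The 2% to 20% already at or below 1.5 on Day 1, and the 40% to 88% reaching a single-score 0.5-point drop with no true change, assume a within-subject SD of 0.2 to 0.6. At an SD of 0.1 the latter is about 4%. These figures show what the event proportions could contain; they do not show that the curves would mainly reflect fluctuation. Type I error and power are essentially unaffected. Requiring confirmation in the main version of this analysis is a matter of choice, not a correction the documents compel.

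**What to change.** In Section 4.8.4, or in the SAP where it restates these definitions:

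1. Rename the 0.5-point event *time to first ACQ-6 response (reduction ≥ 0.5)* and keep the word control for the score bands.
2. Limit the time-to-first partial-control analysis to subjects with a baseline ACQ-6 above 1.5, using the Section 4.3.2.2 boundary, and report how many are left out in each arm.
3. Report the proportion with a reduction of at least 0.5 at Week 52, in line with the ACQ-6 secondary endpoint, instead of at any time over the study. Section 4.8.4.1 already reports AQLQ(S)+12 responders by visit.
4. Optionally, add a sensitivity analysis that counts the 0.5-point event only when it is met at two consecutive two-weekly assessments, dated at the first.

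The cost is wording and a small amount of programming, with no new data. Item 2 removes some subjects from one supportive analysis (2% to 20% under the assumptions above). Because the restriction uses a value measured before the first dose, it does not depend on response to treatment. Item 4 yields fewer events, and an event first seen at the last assessment cannot be confirmed.
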